Testing of Hypotheses: Statistics and Data Analysis

Specific Aim #1: Objective and subjective measures of anxiety will be positively correlated with each other. A primary analysis will examine Pearson correlations between subjective measures of anxiety (i.e., the HDRS Anxiety-Somatization Factor Scale, HAM-A, and CUDOS-A) and eye-blink startle response. Similarly, we will examine correlations between subjective anxiety and reward responsiveness. We will analyze the data to ensure that linearity exists. If linearity does not exist, we will conduct comprehensive sub-analyses to find the best way to characterize the relationship of all data. For example, we will use covariates (e.g., clinical descriptors such as treatment failures) to determine their role in creating non-linearity.

Specific Aim #2: Greater psychophysiological and cognitive objective measures of anxiety will predict better antidepressant response to ketamine, regardless of subjective depression symptoms. We will use a nonlongitudinal linear regression model to assess the extent to which the combination of pre-treatment psychophysiological (e.g., anxiety-potentiated eye-blink startle) and cognitive reward processing (high versus low reward responsiveness) predict the antidepressant treatment response to ketamine (Visits 3 and 4). Antidepressant response to ketamine will be defined as a $\geq 50\%$ improvement in HDRS scores (primary dependent outcome measure).

Specific Aim #3: In ketamine responders, psychophysiological measurements will show a significantly larger decreases in magnitude compared to ketamine nonresponders; greater improvements will be seen in cognitive reward processing measures in ketamine responders. We will use longitudinal analyses (linear mixed effects random regression models) to analyze the effect of ketamine on

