the biomarkers. These models account for the correlation of observations from the same individual. For the change in startle magnitude post-ketamine, the model will include the change in startle magnitude as the outcome, and time (Visit 2 and 4) as the predictor. For the change in reward processing post-ketamine, the model will include the change in reward processing as the outcome, and time (Visit 2 and 4) as the predictor. The coefficient for the correlations in this model quantifies the rate of change in the psychophysiological and cognitive measures associated with a change in depressive symptoms. A coefficient significantly different from zero indicates that changes in the clinical measures of depression are associated with changes in psychophysiological and/or cognitive measures. We will also perform between-group comparisons of measurements for responders vs. nonresponders. All models will be fit using SAS software, $\alpha=0.05$, two-tailed.

Sample Size Determination:

The sample size for Aims #1 and #2 was calculated using the G*Power Sample Size calculator (Version 3.9.1.2; downloaded from <http://www.gpower.hhu.de>) and was based on findings from a *post-hoc* analysis of the antidepressant treatment response to ketamine in anxious versus nonanxious depressed patients, where anxious depression predicted a better response to open-labeled ketamine.(6) The anxious depression effect size (Cohen's *d*) reached its maximum of $d=0.76$ on Day 2 post-infusion. With this, for Aims #1 and #2, we estimate requiring 58 patients with power >0.8 , $r=0.35$ and an $\alpha=0.05$, two-tailed, in order to reject the null hypothesis that there will be no correlations with baseline psychophysiological and cognitive measures between ketamine responders and nonresponders. For Aim #3, a sample size of 58 would allow us to detect a moderately-large effect size (Cohen's $d\geq 0.75$) for between-group comparisons. In order to account for potential drop-outs, we will recruit 70.

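### The Aim #3 mixed models list only time as a predictor, so no listed coefficient measures the depression–biomarker association the plan reads from them

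*Combined protocol and SAP*

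**What the plan says.** The Aim #3 hypothesis, in section VI under Specific Statistical Methods, is that in ketamine responders "psychophysiological measurements will show a significantly larger decreases in magnitude compared to ketamine nonresponders", with a matching statement for reward processing. Section II states the same hypothesis under the broader aim of determining ketamine's effect on the biomarkers.

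The method is given in this order:

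- Model class: "We will use longitudinal analyses (linear mixed effects random regression models) to analyze the effect of ketamine on" the biomarkers. The plan adds that such models allow for correlation between observations on one person.
- Startle: "the model will include the change in startle magnitude as the outcome, and time (Visit 2 and 4) as the predictor".
- Reward: "the model will include the change in reward processing as the outcome, and time (Visit 2 and 4) as the predictor".
- Interpretation: "The coefficient for the correlations in this model" is said to give the rate of biomarker change that goes with a change in depressive symptoms. Then: "A coefficient significantly different from zero indicates that changes in the clinical measures of depression are associated with changes in psychophysiological and/or cognitive measures".
- Separately: "We will also perform between-group comparisons of measurements for responders vs. nonresponders".

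Under Sample Size Determination, Aim #3 is sized on the between-group contrast: "a sample size of 58 would allow us to detect a moderately-large effect size", given as Cohen's d of at least 0.75.

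**The concern.** The two interpretation sentences describe a slope of biomarker change on depression change. Neither model contains HDRS28, HDRS28 change, responder status or any interaction with time. The only listed predictor is time, and its coefficient answers a different question: did the biomarker move, on average, between Visit 2 and Visit 4?

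The difference matters because every participant receives open-label ketamine. An average movement between two test sessions can come from ketamine, but also from habituation, practice or retest effects. An analyst who follows the text exactly would take a significant time effect, whatever its cause, as evidence that biomarker change tracks depression change. An analyst who sees the gap has to supply a term that the plan does not name.

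**Working it through.** **Inputs from the plan.** N = 58; alpha 0.05, two-tailed; biomarkers measured at Visits 2 and 4; HDRS28 collected at all visits; Aim #3 sized at d = 0.75 between groups. The plan gives no expected pre-post shift, responder rate, or correlation between the two changes. Any value used for these below is an assumption.

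**1. The plan's own figure.** Two-sample t-test, assuming 29 responders and 29 nonresponders (the split and the power are not stated for Aim #3):

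- Noncentrality = d × √(n1·n2/(n1+n2)) = 0.75 × √(29·29/58) = 0.75 × 3.808 = 2.856, with 56 degrees of freedom.
- Power = 0.801.

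So 58 patients for d = 0.75 reproduces at 80% power with equal groups. At 20:38 power is 0.76, and at 17:41 it is 0.72. This sizing belongs to the responder comparison and not to the mixed models.

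**2. What the listed model estimates.** Write Y for the biomarker score of patient i at visit t, with time = 0 at Visit 2 and 1 at Visit 4:

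Y_it = b0 + b1·time + u_i + e_it

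With complete data the estimate of b1 is the mean of (Visit 4 − Visit 2). A random-intercept fit to one simulated data set of 58 patients gave a time coefficient of −0.3131 and a mean change of −0.3131. Depression does not enter b1.

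**3. What the interpretation sentences need.** Let H be each patient's HDRS28 change, centred at its mean:

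Y_it = b0 + b1·time + b2·H_i + b3·(time × H_i) + u_i + e_it

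Here b3 is the difference in biomarker change per one-point difference in HDRS28 change, which is the quantity that the plan describes. With two visits and complete data, b3 equals the slope from regressing biomarker change on HDRS28 change. In a second simulated data set of 58 the two slopes were both 0.0339 (t = 0.908 for both). With H centred, b1 stayed equal to the mean change (−0.481). Uncentred, b1 became −0.209, the predicted change at zero HDRS28 change, so centring matters when the time effect is reported.

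**4. How far apart the two tests can be.** Time test with no association present: noncentrality = shift × √58, 57 degrees of freedom, critical value 2.002.

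| Assumed mean shift (SD of change) | Noncentrality | Time test significant |
|---|---|---|
| 0.2 | 0.2 × 7.616 = 1.523 | 32% |
| 0.5 | 0.5 × 7.616 = 3.808 | 96% |

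In simulation with the same kinds of shift, time × HDRS28 change rejected in about 5% of trials, as it should. The reverse case also holds. With no mean shift and a true correlation of 0.5 between the two changes, the time test rejected in 5% of trials and time × HDRS28 change in 98%.

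**The case against.** **A depression term was plainly intended, and the text indicates which.** This stands in large part. A rate of change accompanying a change in symptoms is a slope on a continuous quantity. Study Endpoint names change in the HDRS28 total as the primary clinical endpoint, and the responder contrast has its own sentence. The natural reading is therefore continuous HDRS28 change in the model and responder status in the comparison. A reader might infer a fully open choice between the two, with false positives rising from 5% to about 8% if either result could be reported. The wording does not support that. The 8% comes from running both tests and reporting whichever is significant. Both belong to the natural reading, so naming the missing term would not change that rate; labelling one test as primary would. What remains is that the term is absent from the model as listed.

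**Time answers the stated aim.** It does address ketamine's effect on the biomarkers, as an uncontrolled mean change. But the plan does not interpret the coefficient that way.

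**Aim #3 has its responder comparison.** Correct. A reader might infer that Aim #3 has no valid test, and the documents do not support that. The comparison sentence speaks of measurements where the hypothesis speaks of decreases and improvements, but the hypothesis makes clear that change is meant.

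**With a change score as outcome, time is constant and cannot be estimated.** That is true of the literal wording. However, the plan lists two visits and refers to correlated observations within a person, so repeated scores are the likelier meaning. The point does not depend on the literal reading.

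**Conclusion.** The concern holds in a limited form. Both Aim #3 models omit the term that their interpretation requires, so the inference rule is wrong as written and is not merely short of detail. This follows from the listed terms and rests on no assumed number.

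The 32% and 96% figures show only how different the two questions are. They assume shifts of 0.2 and 0.5 SD of change, no association, 58 complete patients and a literal use of the rule. A reader might take them as the plan's false-positive rate; they are not, because they describe a misapplication under shifts that the documents do not give.

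The consequence is confined to the mixed models. The Aim #3 hypothesis keeps its between-group test, on which the sample size rests. The point should be fixed before analysis; it does not threaten the trial.

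**What to change.** In the Aim #3 paragraph:

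1. Make the outcome the biomarker score at Visits 2 and 4, for startle and for reward processing.
2. Use as fixed effects time, HDRS28 change from Visit 2 to Visit 4 (continuous, centred) and time × HDRS28 change, with a patient random intercept. Visits 2 and 4 are when the biomarkers are measured, and HDRS28 is already collected at both.
3. Name time × HDRS28 change as the coefficient to which the two interpretation sentences refer, and label this model as supporting.
4. Report the time effect only as uncontrolled mean pre-post change.
5. Keep the responder versus nonresponder comparison as the test of the Aim #3 hypothesis, worded as a comparison of change in the biomarker. The hypothesis and the sizing at d of at least 0.75 are both stated between groups.

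Putting time × responder in the mixed model instead would add little. With complete data it equals the two-sample t-test on change already planned (t = −2.717 by both routes in a simulated check), and it would not match the slope that the interpretation sentences describe.

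The cost is analysis-plan wording: no new patients, visits or data.

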This protocol stems from earlier work by the PI with colleagues at the NIH/NIMH on the definition,(3) neurobiology,(4) and treatment(5) of anxious depression. Because anxious depression is a common depressive subtype, we sought to examine the extent to which symptomatically-diagnosed anxious depression predicted response to ketamine. Specifically, in our *post hoc* analysis, we found that patients with anxious depression ($n=15$) had significantly greater antidepressant responses (defined as a $\geq 50\%$ improvement in Montgomery-Asberg Depression Rating Scale (MADRS) scores from baseline) to ketamine compared to patients with nonanxious depression ($n=11$).(6) This

effect was observed over the course of 28 days (see Figure 1; $* = p < 0.05$), with the largest effect at Day 2 (Cohen's $d=0.76$)—a clinically relevant finding, given that anxious depression is typically more difficult-to-treat than nonanxious depression.(5) In addition, patients with anxious depression had significantly longer median days-to-relapse compared to nonanxious depression patients (19.0 ± 17.9 vs 1.0 ± 0.0 days-to-relapse, respectively; $p=0.002$). The two groups did not differ in their experiences with the dissociative ($p=0.62$) or psychotomimetic ($p=0.41$) side effects of ketamine. These results suggested that symptomatically-diagnosed anxious depression may be a clinical predictor of ketamine response, a particularly intriguing finding in the context of the majority of clinical trials involving standard antidepressants in which anxious depression is related to poorer antidepressant response.

[figure not shown]

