Retention: All patients are eligible to receive a free consultation at the DCRP immediately following the completion of all study materials. This care is supplemental to their ongoing care with their treating psychiatrist/doctor. The treating psychiatrist will be informed before any medications changes are considered.

Renumeration: All participants who complete all parts of the study will be paid \$200, and parking will be validated for the study visits. For patients that come in for the screening visit only, they will be renumerated \$20; parking will also be validated. The payment schedule for the other three visits is \$60 each.

Note, the probabilistic reward task is a monetary reward task. Patients will be told that their payment for this task, based on the money they win, will be included in their total payment for study participation.

Procedures for Informed Consent

[figure not shown]
Written informed consent will be obtained by a licensed physician from all patients before protocol-specific procedures begin. The investigator obtaining consent will explain in detail the protocol of the study, its purpose, and potential benefits to the society. Participants will be informed that they can choose to terminate the study at any time, for any reason.

Treatment Assignment and Randomization (If Applicable)

N/A; All participants will be assigned to open-label ketamine.

V. Study Procedures

Research Design Summary: The proposed research (Aims 1-3) will begin with a screening visit (Visit 1) and a medication stabilization period of ≥ 28 days (Phase I). In Phase II, 58 depressed patients meeting research criteria (specified above) will undergo baseline biomarker and psychometric assessments (Visit 2). One-to-two days later, they will receive an open-label infusion of subanesthetic intravenous ketamine (0.5mg/kg over 40 minutes), and will be monitored for 4 hours in the MGH Clinical Research Center (Visit 3). Visit 4, which will occur on the day after the ketamine infusion, will consist of the same biomarker and psychometric assessments from Visit 2 (see “Schema” for overall study outline):

Visits and Parameters to be Measured/Data to be Collected and When the Data is Collected

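### The claim of power above 0.8 for Aims #1 and #2 rests on the largest effect from a small post hoc analysis of different variables; for Aim #1 the effect is unrelated and the stated power is not quite reached

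*Combined protocol and SAP*

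**What the plan says.** Section VI, Sample Size Determination, takes its planning effect from a post hoc comparison of ketamine response in anxious and nonanxious depression. That effect "reached its maximum of $d=0.76$ on Day 2 post-infusion". From it the plan concludes, for Aims #1 and #2 together: "we estimate requiring 58 patients with power >0.8 , $r=0.35$ and an $\alpha=0.05$, two-tailed".

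Section I describes the source: "in our *post hoc* analysis, we found that patients with anxious depression ($n=15" patients, "compared to patients with nonanxious depression ($n=11" patients, with response defined as at least 50% "improvement in Montgomery-Asberg Depression Rating Scale (MADRS) scores from baseline". The effect was followed over 28 days, "with the largest effect at Day 2 (Cohen's $d=0.76".

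The planned tests are these:

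- **Aim #1** (Section VI, Testing of Hypotheses): Pearson correlations of subjective anxiety scales with eye-blink startle and with reward responsiveness.
- **Aim #2** (same section): linear regression of the antidepressant response on pre-treatment startle and reward responsiveness, with response defined on the HDRS.
- **Primary clinical endpoint** (Study Endpoint): change in HDRS-28.
- **Last rating** (Section V, Research Design Summary): "Visit 4, which will occur on the day after the ketamine infusion".

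**The concern.** The value r=0.35 is the source d=0.76 on another scale, not a separate assumption about the biomarkers. It was measured for a different predictor (clinical subtype) and a different scale (MADRS), and it was picked as the largest value over follow-up. For Aim #1 it is not a measure of the same kind of relationship at all, because Aim #1 does not involve treatment response. The documents offer no argument for carrying it over.

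These correlations are the purpose of the study. If the true values are nearer 0.20 to 0.25, the study will miss them more often than it finds them. A null result reported beside a claim of power above 0.8 could then be read as stronger evidence against the biomarkers than it is.

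**Working it through.** **Inputs.** From Sample Size Determination: N=58 (taken here as the number analysed), r=0.35, d=0.76, two-sided alpha 0.05, power above 0.8. From Section I: source groups of 15 and 11.

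**1. Where r=0.35 comes from.** For equal groups, r = d/√(d²+4) = 0.76/√(0.5776+4) = 0.355. With the 15:11 split, 4 is replaced by 26²/(15×11) = 676/165 = 4.097, giving 0.352. So r=0.35 is d=0.76 converted.

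**2. Reproducing 58.** Two-sample t test, 29 per group: noncentrality 0.76×√(29×29/58) = 2.894, 56 df, critical t 2.003, power 0.81. The point-biserial version gives N=58 at r=0.3515 (power 0.802) and N=59 at r=0.35 (power at 58 is 0.799). The plan's figure therefore reproduces for a two-group contrast.

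**3. Aim #1 as a Pearson correlation.** With n=58 the critical correlation is 2.003/√(56+2.003²) = 0.2586, whose Fisher z is 0.2646. Power ≈ Φ{[atanh(r) + r/(2(n−1)) − 0.2646]×√55}, with √55 = 7.416. At r=0.35 this is Φ{(0.3654 + 0.0031 − 0.2646)×7.416} = Φ(0.771) = 0.78. Simulation of the t test on bivariate normal data also gives 0.78. Reaching 0.80 takes 61 patients by this formula and by simulation, or 62 by the plain Fisher formula.

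**4. Power with 58 patients if the correlation is smaller.** The documents give no correlation for startle or reward with either anxiety or ketamine response, so the range is an assumption.

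| Assumed r | Pearson | Point-biserial |
|---|---|---|
| 0.35 | 0.78 | 0.80 |
| 0.30 | 0.64 | 0.65 |
| 0.25 | 0.48 | 0.49 |
| 0.20 | 0.33 | 0.33 |

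The choice of test moves power by at most about 0.02. The assumed correlation moves it by far more.

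**5. Precision of the source effect.** As a simple two-sample comparison, t = 0.76×√(165/26) = 1.91 on 24 df, p = 0.068. The noncentral-t 95% CI for d is -0.05 to 1.56, or r from about -0.03 to 0.61. This is approximate, because the source may have used another model.

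**6. Source effect beside the planned tests.**

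| | Source of d=0.76 | Aim #2 | Aim #1 |
|---|---|---|---|
| Predictor | anxious vs nonanxious subtype | startle, reward | anxiety scales |
| Outcome | MADRS | HDRS | startle, reward |
| Ketamine response involved | yes | yes | no |
| Time | Day 2, largest over 28 days | up to Visit 4, 24 hours after infusion | no post-infusion outcome needed |

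**The case against.** The plan is open about its source: it names the analysis, says the effect is a maximum, and gives r, alpha and sidedness. A reader might infer that the stated power has no basis. That is not so, since a basis is given and 58 follows from it.

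A reader might also infer that the planning effect belongs to a time the trial never observes. Taken literally, Day 2 post-infusion falls after Visit 4. But Section I says only Day 2, and the source's day numbering is not defined. If the infusion day was Day 1, Day 2 is the time of Visit 4. A mismatch is possible but not shown.

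The direction of error is not all one way. If the subtype split cuts a normally distributed anxiety dimension (an assumption), d=0.76 at 15:11 corresponds to a continuous-scale r of about 0.352×0.494/0.392 = 0.44, which is higher than 0.35. It is tempting to go the other way and multiply correlations along a chain from startle through symptom anxiety to response. The protocol posits no such chain: it treats the biomarkers as reflecting underlying circuits. Putting a figure on the inflation from choosing the maximum likewise needs an assumption about how the true effect changes over time, and the documents give none.

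Two lesser points also count for the plan. MADRS is rated at every visit, although HDRS is primary. Expected Outcomes/Results anticipates at least a moderate correlation for Aim #1, which is compatible with 0.35. That is an expectation, though, not a derivation, and the paragraph derives 0.35 from d=0.76.

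What remains untouched is that the effect is a selected maximum for other variables, that nothing connects it to Aim #1, and that Pearson power at r=0.35 is 0.78.

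**Conclusion.** The point holds in limited form. The figure of 58 is arithmetically sound for a two-group contrast at d=0.76. As a power statement for the planned tests it is conditional on an assumption the documents do not support.

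- **Aim #1:** the planning effect is unrelated to the test, and power at r=0.35 is 0.78 rather than above 0.8. The numerical shortfall is small; the missing rationale is the larger fault.
- **Aim #2:** the effect is borrowed from another predictor and another scale. As the largest of several estimates in 26 patients, it tends to overstate. By how much cannot be determined from the documents.

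Power falls to 0.64 at r=0.30, 0.48 at 0.25 and 0.33 at 0.20, assuming 58 analysed patients, bivariate normality and a two-sided 0.05 test. The documents do not establish which of these values is true.

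**What to change.** In the Sample Size Determination paragraph:

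1. Remove Aim #1 from the claim of power above 0.8, or give it a planning correlation of its own with a reason.
2. State that d=0.76 is the largest effect over follow-up for anxious subtype against MADRS, in 15 and 11 patients, and give its confidence interval (about -0.05 to 1.56 as a simple two-sample calculation, or the interval from the source's own model).
3. Replace the single power statement with Pearson power at n=58 over a range: 0.78 at r=0.35, 0.64 at 0.30, 0.48 at 0.25, 0.33 at 0.20.
4. As a secondary matter, define the source's Day 2. If it is later than Visit 4, quote the effect at the matching time if that is available. The documents do not show that it is, and it would still concern subtype and MADRS, so it would not replace items 1 to 3.

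Enrolment, endpoints and analyses stay as they are. The cost is one rewritten paragraph and a less favourable statement of power.

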Patients will be excluded if any of the following criteria are met:

- 1) delirium or dementia diagnosis,
- 2) unstable medical illness or clinically significant laboratory results,
- 3) history of clinically significant cardiovascular disease or electrocardiogram (EKG) findings, or medical conditions that put the patient at risk for possible cardiac side effects (e.g., requirement of cardiac pacemaker) or alter brain morphology (e.g., recent head trauma, post intracranial surgery, intracranial mass or bleed or unstable sleep apnea), or a blood pressure $>140/95$ mmHg at Screening,
- 4) history of multiple adverse drug reactions, (e.g., history of hives or anaphylaxis in response to a medication, severe intolerance and/or severe side effects to a medication), including hypersensitivity to ketamine,
- 5) current/past history of psychotic disorders, history of out-of-body feelings or derealization,
- 6) active substance use disorders (except nicotine and caffeine) within the past six months or past history of ketamine/PCP abuse (we will confirm this with collateral information from their doctor if necessary),
- 7) requirement of excluded medications that may interact with ketamine (see exclusionary medications list),
- 8) caffeine or nicotine use within 1 hour of psychophysiology testing, or alcohol use within 1 day of testing,
- 9) pregnancy, breastfeeding, or unacceptable means of birth control (females only)
- 10) clinically significant hearing impairment,
- 11) current serious suicidal or homicidal risk,
- 12) concurrent participation in other research studies involving medications or other treatments,
- 13) narrow angle glaucoma,
- 14) acute intermittent porphyria history,
- 15) history of seizures in the past 6 months, regardless of seizure type,
- 16) hyperthyroidism or untreated hypothyroidism,
- 17) airway instability or pulmonary disease with hypercarbia, or
- 18) current or past cubital or carpal tunnel syndrome.

IV. Participant Enrollment

We will enroll 58 depressed patients outpatients into the study.

Recruitment: 58 outpatients will be enrolled via response to flyers, advertisements, e-mails, participation in previous studies with an interest in participating in further research, and letters to providers. The DCRP has used these methods for over two decades with considerable success, receiving an average of over 35 phone calls/week.

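### The plan gives two numbers to enrol (58 and 70); if enrolment stops at 58, Aims #2 and #3 lose their stated power, and the Pearson test of Aim #1 has 78% rather than more than 80% at r=0.35.

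*Combined protocol and SAP*

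**What the plan says.** Sample Size Determination in Section VI starts from an earlier comparison of anxious and nonanxious patients, in which the effect size "reached its maximum of $d=0.76$ on Day 2 post-infusion". From this the plan concludes, for Aims #1 and #2 together, that "we estimate requiring 58 patients with power >0.8", with r=0.35 and two-sided alpha 0.05. The null hypothesis is worded as "no correlations with baseline psychophysiological and cognitive measures between ketamine responders and nonresponders". For Aim #3, 58 patients are said to detect a Cohen's d of 0.75 or more between groups. The paragraph ends: "In order to account for potential drop-outs, we will recruit 70". No drop-out rate is given.

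The analyses are set out under Specific Statistical Methods. For Aim #1, "A primary analysis will examine Pearson correlations between subjective measures of anxiety" and eye-blink startle. For Aim #2, "We will use a nonlongitudinal linear regression model to assess the extent to which the combination of pre-treatment psychophysiological" and reward measures predicts response. Aim #3 includes a comparison of responders with nonresponders.

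The number to enrol appears elsewhere too. Section IV (Participant Enrollment) states 58 twice, the second time as "58 outpatients will be enrolled via response to flyers". The Research Design Summary in Section V has 58 patients undergoing the Visit 2 baseline assessments.

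**The concern.** A coordinator working from Section IV would close enrolment at 58. One working from Section VI would continue to 70. The power statement needs 58 patients with usable data, so only the second course leaves room for loss.

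The plan itself foresees loss. Section V lets patients withdraw during the shock work-up, and withdraws those who have serious adverse events or need rescue medication at the infusion. Aims #2 and #3 need post-infusion data and so bear most of it.

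The second issue is that one power figure covers two different analyses. The stated null concerns responders and nonresponders, but Aim #1 correlates two continuous measures and involves neither group. A null result would be read against the printed power, so that power should belong to the test actually used.

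**Working it through.** **Inputs.** From Sample Size Determination: d=0.76, r=0.35, two-sided alpha 0.05, 58 required, 70 recruited, d of 0.75 for Aim #3. From Sections IV and V: 58 enrolled, 58 at Visit 2. Assumed, because the plan gives neither: the loss rate and the responder split.

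**1. Reproducing the 58.** For a two-sample t-test the noncentrality is d × sqrt(n1·n2/(n1+n2)).
- 29 per group: 0.76 × sqrt(29·29/58) = 0.76 × 3.808 = 2.894. With 56 df and critical t 2.003, power is 0.812.
- 28 per group: power 0.798.

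So 58 is the smallest equal-group total above 0.80. In correlation form, r = d/sqrt(d²+4) = 0.76/2.140 = 0.355, which the plan prints as 0.35. With noncentrality sqrt(n·r²/(1−r²)), the two-group (point-biserial) model gives:
- r=0.355: power 0.811 at n=58; smallest n for 0.80 is 57.
- r=0.35 exactly: power 0.7985 at n=58; smallest n is 59.

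The margin is therefore one patient at d=0.76 and nothing at the printed r.

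**2. If enrolment stops at 58.** Going from 70 to 58 implies a loss of 12/70 = 17.1%. Applied to 58 enrolled, 58 × 58/70 = 48.06, so 48 are analysed.
- d=0.76, 24 per group: noncentrality 0.76 × sqrt(24·24/48) = 0.76 × 3.464 = 2.633; power 0.73.
- r=0.35: noncentrality sqrt(48 × 0.1225/0.8775) = 2.589; power 0.72.
- Aim #3, 24 per group: 80% power needs a noncentrality of about 2.862, so the detectable d is 2.862/3.464 = 0.83, against the stated 0.75.

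Over a range of assumed losses, two-group power at r=0.35 is:

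| Loss | Analysed | Power |
|---|---|---|
| 0% | 58 | 0.80 (0.7985) |
| 10% | 52 | 0.75 |
| 17% | 48 | 0.72 |
| 20% | 46 | 0.70 |

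**3. Aim #1 with its own test.** Pearson correlation, r=0.35, n=58, Fisher z with bias term:
- Critical r = 2.003/sqrt(56 + 2.003²) = 0.2586, and atanh(0.2586) = 0.2646.
- Expected z = atanh(0.35) + 0.35/(2 × 57) = 0.3654 + 0.0031 = 0.3685.
- (0.3685 − 0.2646) × sqrt(55) = 0.771, so power is 0.780.

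The exact bivariate-normal calculation gives 0.781 and simulation 0.780. For 0.80, 61 patients are needed; with 58, the smallest r with 80% power is 0.358. Using the unrounded r of 0.355, power at 58 is still 0.793.

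**4. Unequal responder groups, 58 analysed.** At 56 df, 80% power needs a noncentrality of about 2.851. Dividing by sqrt(n1·n2/58) gives the detectable d. The last column uses noncentrality 0.76 × the same factor.

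| Split (assumed) | Factor | Detectable d | Power at d=0.76 |
|---|---|---|---|
| 29:29 | 3.808 | 0.75 | 0.81 |
| 20:38 | 3.620 | 0.79 | 0.77 |
| 14:44 | 3.259 | 0.87 | 0.68 |

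**The case against.** The best defence is that 58 is sound. It follows exactly from the plan's own d=0.76 with 29 per group, and the two-group model fits a null about responders and nonresponders. That stands. A reader might infer an arithmetic slip from the Pearson result, but the documents do not support that: the calculation is right for a two-group comparison and has been carried over to Aim #1, where it does not fit.

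The Aim #1 gap is also small: about 2 percentage points, 3 patients, or 0.35 against 0.358 in detectable r. The assumed effect comes from a post hoc comparison of 15 and 11 patients, taken at its largest time point, so its own uncertainty is far greater. That stands too.

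A reader might also infer that Aim #1 falls to about 0.70, the Pearson power with 48 analysed. The documents do not support this as a finding. The 17% is inferred, and the Aim #1 correlations can be computed from Visit 2 data, where Section V places 58 patients. Withdrawal during the shock work-up could cost Aim #1 some observations, but nothing in the plan puts that at 17%.

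Finally, 70 may have been meant as the number recruited to yield 58 at Visit 2. That is possible, but the plan does not say so. Even then, 58 at Visit 2 leaves no allowance for later loss in Aims #2 and #3.

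**Conclusion.** The conflict between 58 enrolled and 70 recruited is real and is the weightier half of the point. If 58 is the cap, two-group power for Aim #2 falls to about 0.72 (r=0.35) or 0.73 (d=0.76, equal groups), given a 17% loss that is inferred rather than stated. Losses of 10% to 20% give 0.75 to 0.70 at r=0.35. These figures treat Aim #2 as a single two-group comparison, as the sample size paragraph does, whereas the planned analysis is a regression on a combination of predictors. If 70 are recruited and 58 analysed, this problem disappears.

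For Aim #1 the stated power of more than 0.8 should read 0.78 at r=0.35. This is a small correction.

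The Aim #3 figure is correct for equal groups. Response is an outcome, so the design cannot fix the split, and the plan gives no expected response rate. The splits shown are illustrations.

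**What to change.** - Make Section IV, the Research Design Summary in Section V and Sample Size Determination agree that 70 are recruited so that 58 are analysed, and state the assumed drop-out rate.
- Restate Aim #1: 58 analysed patients give 78% power for a Pearson r of 0.35 (80% for r of 0.36).
- Say that 58 comes from a two-group calculation at d=0.76, and name the G*Power model used.
- State that the Aim #2 and Aim #3 figures assume equal numbers of responders and nonresponders, and give the detectable d for other splits: 0.75 at 29:29, 0.79 at 20:38 and 0.87 at 14:44, marked as assumed.

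The cost is wording and slightly less favourable stated figures. No patients beyond the planned 70 are needed.
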